3.1.2 Phase 2 Study Design

The primary objective of study Part 2 is to further evaluate safety and efficacy of the combination dose in the 4 selected CRC, pancreatic cancer and NSCLC subject groups. Other tumor types may be explored based on emerging data. The dose or doses to be evaluated in Part 2 will be based on results from Part 1. Part 2 will begin after safety of the dose level(s) explored in Part 1 has been assessed and determined to be safe.

Part 2 will include 6-9 subjects from Part 1 who have been treated with the recommended combination dose, and will enroll additional CRC, pancreatic cancer and NSCLC subjects following a Simon two-stage design: stage 1 will enroll up to 67 subjects overall, stage 2 may add another 118 subjects as per the rules described below. The recommendations to enroll stage 2 are based on ORR (see rules described below); nonetheless, the DLRT (see [Section 6.2.1.2.1](#)) will make decisions after reviewing all available safety, efficacy, pharmacokinetic and pharmacodynamic data. Analysis of data in Part 2 will be done separately for each group (Group 1, 2, 3, 4a, 4b).

- Group 1 will enroll up to 43 advanced MMR-proficient CRC subjects who are naïve to anti-PD-1/PD-L1/CSF-1/CSF-1R therapies. Eighteen (18) subjects will be enrolled during the first stage and treated with the AMG 820 plus pembrolizumab combination. If 2 or fewer subjects have an objective response per irRECIST then,

depending on the review of all available data, further enrollment may be discontinued; otherwise, enrollment up to 43 subjects will occur.

- Group 2 will enroll up to 29 advanced pancreatic cancer subjects who are naïve to anti-PD-1/PD-L1/CSF-1/CSF-1R therapies. Ten (10) subjects will be enrolled during the first stage and treated with the AMG 820 plus pembrolizumab combination. If no subjects have an objective response per irRECIST then, depending on the review of all available data, further enrollment may be discontinued; otherwise, enrollment up to 29 subjects will occur.

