6.2.1.2.5 Cohort Dose Level Determination

Study Part 1

A Dose Level Review Team (DLRT) will convene before a decision is made to open study Part 2. At the start of Part 1, enrollment of the first cohort of 6 to 9 evaluable patients will open for enrollment with a starting dose of AMG 820 1400 mg plus pembrolizumab 200 mg Q3W. Following subject completion of the DLT period, the DLRT will review all available safety data for the first cohort. If the data supports continued dosing at the selected starting dose, study Part 2 will be initiated at the same dose level. If it is determined that the starting dose is non-tolerable (if 33% or more of the evaluable subjects experience a DLT), dose de-escalation will occur and a second Part 1 cohort will be enrolled to test a decreased dose of AMG 820 in combination with 200 mg pembrolizumab Q3W. This will occur until identification of a well-tolerated dose for study Part 2. The AMG 820 (mg) pre-specified nominal cohort dose levels to be explored are 1100 mg and 800 mg Q3W. The pembrolizumab dose level will remain at 200 mg Q3W.

Part 2

Part 2 will have 4 groups, which will be evaluated using a Simon two-stage design:

Table 1. Study Part 2 Subject Groups

Naïve to anti-PD-1/PD-L1/CSF-1/CSF-1R treatment	
Group 1	CRC ^{MMR-proficient}
Group 2	Pancreatic Cancer
Group 3	NSCLC ^{PD-L1 low}
Refractory/ relapsing on anti-PD-1/PD-L1 + naïve to CSF-1/CSF-1R treatment	
Group 4a	NSCLC ^{PD-L1 low}
Group 4b	NSCLC ^{PD-L1 high}

The dose or doses (proposed recommended phase 2 dose, RP2D) to be evaluated in part 2 of the study will be based on results from part 1. The DLRT may determine the RP2D, which is defined as a dose(s) that is/are safe and produces pharmacodynamic effects. Emerging safety data may be used to re-challenge the selected dose in Study Part 1. If the initially selected dose is re-challenged, additional subjects may be enrolled in the corresponding cohort. In addition, the study may be discontinued or modified at any time due to documented safety findings.

Enrollment into the second stage of the Simon two-stage design will be determined by results through Study Part 2 stage 1.

All dose level and enrollment decisions will be formally communicated to investigators via a memorandum.

The dosing schedule is described by a [schema](#) in the protocol synopsis.

6.2.1.3 Dosage Adjustments, Delays, Rules for Withholding or Restarting, Permanent Discontinuation: AMG 820

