10.2 Sample Size Considerations

It is anticipated that 67 to 197 subjects will be enrolled overall in this study.

Part 1 will enroll 6 to 18 evaluable subjects. The sample size in Part 1 is based on practical consideration, and it is consistent with conventional oncology studies with the objective to evaluate the safety and tolerability of a treatment combination. With 6 subjects in a cohort, there is a 47-91% probability of observing at least one DLT if the true DLT rate is 10-33%.

Part 2 evaluation of efficacy will include at least 6 subjects from part 1 who have been treated with the recommended combination dose, and will enroll additional CRC, pancreatic cancer and NSCLC subjects up to maximum 185 subjects overall. The sample size in each group evaluated in Part 2 is chosen to test whether AM820 can enhance the anti-tumor activity observed historically with pembrolizumab alone and/or overcome lack of response to pembrolizumab monotherapy. For each group and sub-group enrollment may stop early due to insufficient clinical activity. The pre-planned recommendation for early termination is based on ORR (evaluated when the subjects complete at least 6 months of treatment or earlier if already reaching the recommended number of responders), nonetheless the DLRT (see [Section 6.2.1.2.1](#)) will make the decision for early termination after reviewing all available safety, efficacy, pharmacokinetic and pharmacodynamic data.

Group 1 will consist of up to 43 subjects with MMR-proficient CRC (only 18 enrolled initially in the first stage) who are naïve to anti-PD-1/PD-L1/CSF-1/CSF-1R treatment. In [2015, Le et al](#) reported a pembrolizumab objective response rate (ORR) per RECIST1.1 and irRC of 0% (0 of 18 patients) for MMR-proficient colorectal cancers. It is anticipated that the combination treatment of AMG 820 and pembrolizumab will have an ORR of 25% or higher in MMR-proficient CRC tumors; an ORR of 10% or less is considered to be insufficient anti-tumor activity to warrant future research. If 2 or fewer of the initial 18 subjects have an objective response then the recommendation is for enrollment to Group 1 be stopped for futility. If 8 or more of the 43 subjects have an objective response then the true ORR is determined to be >10%. This Simon Two-Stage design provides 80% power when the true ORR is 25% while maintaining a 1-sided, 5% alpha error when the true ORR is 10% or lower.

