Group 2 will consist of up to 29 subjects with advanced pancreatic cancer (only 10 enrolled initially in the first stage) who have not received prior treatment with a PD-1/PD-L1/CSF-1/CSF-1R inhibitor. In [2012, Brahmer et al](#) reported a pembrolizumab ORR of 0% (0 of 14 patients) for pancreatic cancer. It is anticipated that the combination treatment of AMG 820 and pembrolizumab will have an ORR of 20% or higher in pancreatic tumors; an ORR of 5% or less is considered to be insufficient anti-tumor activity to warrant future research. If none of the initial 10 subjects have an objective response then the recommendation is for enrollment to Group 2 be stopped for futility. If 4 or more of the 29 subjects have an objective response then the true ORR is determined to be >5%. This Simon Two-Stage design provides 80% power when the

true ORR is 20% while maintaining a 1-sided, 5% alpha error when the true ORR is 5% or lower.

Group 3 will consist of up to 55 subjects (only 19 enrolled initially in the first stage) with NSCLC who have not received prior treatment with a PD-1/PD-L1/CSF-1/CSF-1R inhibitor, and who have tumor PD-L1 expression <50%. [Garon et al in 2015](#) reported a pembrolizumab ORR per RECIST1.1 of 13.1% (28 of 214 patients) for NSCLC patients with tumor PD-L1 expression <50%, and an ORR of 14.4% (21 of 146 patients) for those with tumor PD-L1 expression from 1% to 49%. It is anticipated that the combination treatment of AMG 820 and pembrolizumab will have an ORR of 30% or higher in low PD-L1 expressing subjects; an ORR of 15% or less is considered to be insufficient anti-tumor activity to warrant future research. If 3 or fewer of the initial 19 subjects have an objective response then enrollment to Group 3 will be stopped for futility. If 13 or more of the 55 subjects have an objective response then the true ORR is determined to be >15%. This Simon Two-Stage design provides 80% power when the true ORR is 30% while maintaining a 1-sided, 5% alpha error when the true ORR is 15% or lower.

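### The stated 1-sided 5% alpha holds only if the stage-1 stops are followed; as written, with advisory stops and unconditional final cut-offs, the Part 2 rule allows up to 5.5–6.1%

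*Protocol*

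**What the plan says.** Protocol 10.2, repeated in SAP 3.2, gives each Part 2 group a Simon two-stage design with 80% power and a 1-sided 5% error rate. For Group 1 the claim is that the design works "while maintaining a 1-sided, 5% alpha error when the true ORR is 10% or lower".

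**The stage-1 stop is advisory.** For Group 1 with 2 or fewer responders among 18, "then the recommendation is for enrollment to Group 1 be stopped for futility". The same section says that the DLRT "will make the decision for early termination after reviewing all available safety, efficacy, pharmacokinetic and pharmacodynamic data". Protocol 3.1.2 says that, "depending on the review of all available data, further enrollment may be discontinued; otherwise, enrollment up to 43 subjects will occur". Protocol 10.3.1 and SAP 8.1 likewise leave stage-2 enrollment to the DLRT. One sentence, in Protocol 6.2.1.2.5, leans more towards the data: "Enrollment into the second stage of the Simon two-stage design will be determined by results through Study Part 2 stage 1".

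**The final rule is unconditional.**
- Group 1: "If 8 or more of the 43 subjects have an objective response then the true ORR is determined to be >10" (per cent).
- Group 2: "If 4 or more of the 29 subjects have an objective response then the true ORR is determined to be >5" (per cent); Groups 4a and 4b have the same rule per sub-group.
- Group 3: "If 13 or more of the 55 subjects have an objective response then the true ORR is determined to be >15" (per cent).

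None of these requires that the stage-1 criterion was met. Neither document says how to judge a group that was continued after failing it.

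**Two wordings differ between sections.**
- Group 3: Protocol 10.2 and SAP 3.2 make the stop mandatory; Section 3.1.2 of both documents makes it permissive.
- Group 4: Protocol 10.2 and SAP 3.2 apply the rule separately to 4a and 4b. The synopsis and Section 3.1.2 of both documents refer loosely to either sub-group, followed by enrollment up to the combined 58.

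**The concern.** A Simon design declares success only when two things happen: the group passes stage 1, and the total reaches the final cut-off. The 5% belongs to that joint event. This plan makes the first condition optional and leaves it out of the second. A group could fail stage 1, be continued by the DLRT, reach the final count and be declared better than its null. The stated error rate does not cover that path.

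At stake is whether that declaration is permitted and which error rate attaches to it. The situation is not remote. At exactly the null rate, failing stage 1 is the more likely result: 73% in Group 1, 60% in Groups 2, 4a and 4b, and 68% in Group 3.

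**Working it through.** **Inputs** (Protocol 10.2, SAP 3.2)

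| Group | n1 | Fail stage 1 if ≤ r1 | n | Success if ≥ R | p0 | p1 |
|---|---|---|---|---|---|---|
| 1 | 18 | 2 | 43 | 8 | 10% | 25% |
| 2, 4a, 4b | 10 | 0 | 29 | 4 | 5% | 20% |
| 3 | 19 | 3 | 55 | 13 | 15% | 30% |

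**Step 1. Reproduce the plan's figures, with stops followed.**
P(success) = Σ over x1 > r1 of P(X1 = x1) × P(X2 ≥ R − x1), where X1 ~ Bin(n1, p) and X2 ~ Bin(n − n1, p).

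| Group | Alpha at p0 | Power at p1 |
|---|---|---|
| 1 | 4.80% | 80.0% |
| 2, 4a, 4b | 4.68% | 80.1% |
| 3 | 4.77% | 80.1% |

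The stated 5% and 80% are confirmed for the designs with their stops applied.

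**Step 2. Maximum alpha under the written rule.** If every failed stage 1 is overridden and the same cut-off is used, alpha is P(Bin(n, p0) ≥ R).

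| Group | Maximum alpha | Excess over Step 1 | Excess over 5% |
|---|---|---|---|
| 1 | 6.07% | 1.27 points | 1.07 points |
| 2, 4a, 4b | 5.48% | 0.79 points | 0.48 points |
| 3 (permissive wording only) | 6.03% | 1.27 points | 1.03 points |

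Excesses are taken before rounding. Groups 2, 4a and 4b give a simple check, because failing stage 1 means exactly 0 of 10. The added term is 0.95^10 × P(Bin(19, 0.05) ≥ 4) = 0.5987 × 0.0132 = 0.0079, which takes 4.68% to 5.48%.

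**Step 3. How much overriding is needed to pass 5%.** If a fraction q of failed stage-1 results is overridden, independently of the response count, alpha = followed + q × (maximum − followed). Setting this to 5%:
- Group 1: q = (0.0500 − 0.0480) / (0.0607 − 0.0480) = 0.157
- Groups 2, 4a, 4b: q = (0.0500 − 0.0468) / (0.0548 − 0.0468) = 0.400
- Group 3: q = (0.0500 − 0.0477) / (0.0603 − 0.0477) = 0.183

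(The ratios use unrounded values.)

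**Step 4. Overrides that depend on the count.** If only groups one response short of passing are continued:
- Group 1 (2/18): 0.0480 + 0.2835 × 0.0334 = 5.75%
- Group 3 (3/19): 0.0477 + 0.2428 × 0.0351 = 5.62%

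In Groups 2, 4a and 4b, 0/10 is the only failing count, so the figure is the Step 2 maximum.

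**Step 5. Group 4 wording.** Suppose a response in one sub-group lets both continue. The Step 2 term for a sub-group with 0/10 then applies only when the other has a response: 0.0468 + 0.0079 × (1 − 0.5987) = 5.0% per sub-group. The wording matters little for alpha, but the stated figures rest on the per-sub-group rule.

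**The case against.** The strongest reply is that the sentence is right as it stands. It attributes the 5% to a Simon two-stage design, and such a design includes its stage-1 stop. The DLRT's discretion is stated openly and repeatedly, including in the section that gives the alpha, and Protocol 6.2.1.2.5 has stage-2 enrollment follow from stage-1 results. For Group 3, Protocol 10.2 makes the stop mandatory.

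The effect is also small. After a failed stage 1 at the null, the chance of still reaching the cut-off is 1.7% (Group 1), 1.3% (Groups 2, 4a, 4b) and 1.9% (Group 3). The nulls lie above the historical rates the plan cites: 10% against 0 of 18, 5% against 0 of 14, and 15% against 13.1%. At a true rate of 13.1%, Group 3 with every stop overridden succeeds only 2.3% of the time.

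Most of this stands and limits the weight of the point. It does not remove the gap. Disclosing who decides is not the same as saying what may be concluded after an override, and the plan is silent on that. Advisory futility is common and acceptable when the final rule holds its level with the stops ignored, or when success requires passing stage 1. Here neither is so.

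Three stronger readings are tempting, and the documents do not support them.
- *The designs were miscalculated.* They were not; Step 1 reproduces the stated figures.
- *The trial's type I error is 6%.* That is a ceiling, reached only if every failed stage 1 is overridden at exactly the null.
- *The planned primary analysis is an inflated test.* The cut-offs appear only in the sample-size text. Protocol 10.4.2 and SAP 10.6.1 plan a response proportion with 90% and 95% confidence intervals.

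**Conclusion.** The point holds as a minor error in a stated property. The 5% is a true ceiling for the Simon designs with their stops followed (4.80%, 4.68%, 4.77%), but not for the rule as written, which allows up to 6.07% in Group 1 and 5.48% in Groups 2, 4a and 4b. For Group 3 the bound is 6.03%, and only if the permissive wording of Section 3.1.2 governs.

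The excess over 5% is at most 0.5 to 1.1 points. Alpha stays at or below 5% if overrides unrelated to the response count are rarer than about 16% (Group 1), 40% (Groups 2, 4a, 4b) and 18% (Group 3). Overrides concentrated on near-misses reach 5% sooner.

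These figures assume full enrollment to n, unchanged cut-offs and a true rate equal to the null. Practical consequences are further limited because the Amendment 2 rationale records that the sponsor has decided to stop investigating the combination. The final report still needs a defined rule for any group continued after failing stage 1.

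**What to change.** 1. In Protocol 10.2 and SAP 3.2 and 8.1, add: *A group continued after failing its stage-1 criterion is reported descriptively and cannot be declared to exceed its null ORR.* This keeps the DLRT's discretion and restores the 5% ceiling. If the sponsor wants to keep the possibility of a positive declaration, restate the maximum alpha as 6.1% (Group 1), 5.5% (Groups 2, 4a, 4b) and 6.0% (Group 3).
2. Reconcile the Group 3 stopping wording in Protocol 10.2 and SAP 3.2 with that in Section 3.1.2 of both documents.
3. Align the Group 4 wording in the synopsis and in Section 3.1.2 of both documents with the per-sub-group rule in Protocol 10.2 and SAP 3.2.

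The cost is one sentence and two wording alignments, with no change to sample size or cut-offs. The price is either that a group continued after failing stage 1 cannot be claimed positive, or that the stated alpha is slightly less favourable. Raising each cut-off by one is a poor substitute: maximum alpha would fall to 2.4%, 1.4% and 3.0%, but power with stops followed would fall to 73.0%, 68.1% and 74.7% (Group 1; Groups 2, 4a, 4b; Group 3).

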10.3 Planned Analyses

10.3.1 Interim Analyses

Safety and all clinical data will be monitored on an ongoing basis. All available cumulative data will be reviewed in Part 1 by cohort, prior to making dose escalation decisions, by the Dose Level Review Team (DLRT, see [Section 6.2.1.2](#)). In study Part 2

stage 1, similar assessments will be held after each set of 20 subjects have enrolled through the end of Part 2 stage 1 enrollment.

In Part 2, a Simon Two-Stage design is used for all groups (Group 1-3, 4a, 4b) with the first stage enrolling n=18, 10, 19, 10 and 10 subjects, respectively (see [design schema](#)). Each group will enroll subjects to a first stage. The second stage for each group will be enrolled depending on clinical activity from stage 1, evaluated when the subjects have been treated for at least 6 months or earlier if the required number of responders have been reached (see [Section 10.2](#) for details). The pre-planned recommendations for enrollment to stage 2 are based on ORR per local irRECIST, however the DLRT will make the decisions for stage 2 enrollment after reviewing all available safety, efficacy, pharmacokinetic and pharmacodynamic data.

10.3.2 Dose Level Review Team (DLRT)

Dose Level Review Meetings (DLRMs) will be held to review data, monitor safety, and make decisions on dose escalation / change decisions. The DLRT will be composed of the investigators or designees, and the following Amgen representatives: medical monitor, early development leader, global safety officer or designee, clinical study manager, biostatistician and clinical pharmacologist. Additional members may be added as needed. The following members are responsible for DLRT decisions: investigators, Amgen medical monitor, and global safety officer or designee. Study decisions by DLRM participants must be unanimous. All available study data, including data collected after the initial DLT window, and including demographics, IP administration, medical history, concomitant medications, adverse events, ECGs, vital signs, laboratory data, efficacy and PK/PD information will be reviewed. In addition to DLTs, all \geq grade 3 toxicities not meeting DLT criteria will be reviewed and may be considered in DLRT decisions. The study may be discontinued or modified at any time due to documented safety findings.

All DLRM requirements are outlined in the protocol. A DLRM Charter will not be used.

10.3.3 Primary Analysis

The primary analysis (primary and secondary endpoints) may be done separately for each group (eg, if the pancreatic cancer group completes target enrollment months ahead of the other cancer groups, analysis for Group 2 would be executed):

1. At 6 months: once the target enrollment is complete and each subject has been treated for at least 6 months or responded or withdrawn from the study, the analysis of the primary endpoints will occur.
2. At 12 months: once the target enrollment is complete and each subject has been treated for at least 12 months or has been followed up for PFS and OS for 12 months or withdrawn from the study, the analysis of primary and secondary endpoints (safety endpoints, ORR, PFS and OS at 6 and 12 months) will occur

10.3.4 Final Analysis

A final analysis is planned after all subjects from Part 1 and Part 2 have ended the study.

10.4 Planned Methods of Analysis

10.4.1 General Considerations

Descriptive statistics will be provided for selected demographics, safety, PK, PD and biomarker data by dose, dose schedule, and time as appropriate. Descriptive statistics on continuous data will include means, medians, standard deviations and ranges, while categorical data will be summarized using frequency counts and percentages. Graphical summaries of the data may also be presented. Analysis of data in Part 2 will be done separately for each group (Group 1, 2, 3, 4a, 4b).

10.4.2 Primary Efficacy Endpoint

For subjects treated at the maximum tolerated combination (combining subjects from Part 1 and Part 2), the proportion of subjects with OR (a complete or partial response to treatment) per irRECIST with corresponding 90% and 95% CI will be calculated and tabulated.

10.4.3 Secondary Efficacy Endpoint(s)

The following analyses will be done using secondary efficacy endpoint data for all subjects treated at the maximum tolerated combination (combining subjects from Part 1 and Part 2). The proportion of subjects with OR per RECIST 1.1 and corresponding 90% and 95% CI will be calculated and tabulated. Using the Kaplan Meier estimate, the PFS at 6 and 12 months and the OS at 6 and 12 months with corresponding 90% CI will be tabulated. Listings will be produced for all subjects indicating the OS, PFS, TTR, DOR and TTP. Kaplan Meier curve will be presented for OS, PFS, TTR, DOR and TTP with estimates for rates and 80% CI at selected weeks.

10.4.4 Safety Endpoints

Unless otherwise specified, statistical analyses on safety endpoints will be done using subjects from the Safety Analysis Set, which includes subjects that are enrolled and received at least 1 dose of AMG 820.

10.4.4.1 Adverse Events

Subject incidence of all treatment-emergent adverse events will be tabulated by system organ class and preferred term. The number and percentage of subjects reporting adverse events will be evaluated overall and by AMG 820 dose level and will also be tabulated by relationship to AMG 820. Tables of dose limiting toxicities, fatal adverse events, serious adverse events, adverse events leading to withdrawal from investigational product or other protocol-required therapies, and significant treatment-emergent adverse events will also be provided.

10.4.4.2 Clinical Laboratory Tests

Clinical chemistry, hematology, and urinalysis data will be listed and reviewed for each subject. Values outside the normal laboratory reference ranges will be flagged as high or low on the listings. Depending on the size and scope of changes in laboratory data, summaries of laboratory data over time and/or changes from baseline over time may be provided. Tables of maximum shifts from baseline for selected laboratory values may also be provided.

